**Table 2-4 Rules for selecting values for analysis**

Timing of measurement	Type of data	Rule
Baseline	All data	The last measurement prior to first dose – note this may include measurements taken on the day of randomization (e.g. lab).
Post-baseline safety	Summary visit information (e.g. lab, ECG, vital etc.)	
The (non-missing) measurement closest to the target day will be used.
 
In the event two measurements are taken equally apart (e.g. 1 day before target date and 1 day after) the first one will be used.
 
If two measurements are taken on the same day then select the first one (using the time).
 
If two measurements are taken on the same date/time then use the first visit number (assuming this is the planned visit).
 
If two measurements are taken on the same date/time/CRF visit then use the average of two assessments

Post-baseline efficacy	All data except DLQI, EQ-5D and health assessment, PGIC	
The measurement closest to the target day will be used. In the event two measurements are taken equally apart (e.g., 1 day before target date and 1 day after), the earlier one will be used.
 
If two measurement are taken on the same day then select the first one using eCRF visit number.

Post-baseline safety	Summary visit information (e.g. laboratory values, vital signs, etc.)	
The (non-missing) measurement closest to the target day will be used. In the event two measurements are taken equally apart (e.g., 1 day before target date and 1 day after), the earlier one will be used.
 
If two measurements are taken on the same day then select the first one (using the time).
 
If two measurements are taken on the same date/time then use the first eCRF visit number (assuming this is the planned visit). If two measurements are taken on the same date/time/eCRF visit number then take the average value of these two results.

Post-baseline safety	Notable abnormalities (e.g.	The most extreme measurement in the window

---

Timing of measurement	Type of data	Rule
and efficacy	vital signs, PGIC) and CTCAE grading for laboratory values	will be used. Note this means a subject can have a notably high and notably low measurement within a window
Post-baseline efficacy	FDG –PET scan Cardiometabolic biomarker	Data will be analyzed as per CRF captured visit Data will be analyzed as per CRF captured visit but for discontinued patients only discontinued visit will be mapped to the next visit of the last available assessment before discontinuation within the same treatment period

---

## 2.4.2 Prior, concomitant and post therapies

Prior or concomitant medication will be identified based on recorded or imputed start and end dates of medication taken, as follows:

**Prior medication:** Treatments taken and stopped prior to first dose of study treatment.

**Concomitant medication:** Any medication administered at least once between the day of first dose of randomized study treatment and the last day of study visit (including those which were started pre-baseline and continued into the treatment period), other than study medication, will be considered as concomitant medication.

Concomitant medications excluding tropical corticosteroid will be summarized.

Medications will be identified and presented in alphabetical order, using Novartis drug and therapy dictionary (NovDTD) and by Anatomical Therapeutic Chemical (ATC) codes and grouped by anatomical main group (the first level of the ATC codes).

Prior, concomitant medications will be summarized by treatment using frequency counts and percentages for Safety Set, in separate tables.

Tables will also show the overall number and percentage of subjects receiving at least one drug of a particular ATC code and at least one drug in a particular anatomical main group. In addition, concomitant use of tropical corticosteroid will be summarized separately by treatment.

Treatment use for indication, dose and date of administration will be listed. Duration of exposure will be presented by treatment if treatment is stopped during study period. Ongoing treatments will be flagged.

## 2.5 Analysis of the primary objective

### 2.5.1 Primary efficacy variable

The primary efficacy variable is the change from baseline in the target (arterial vascular uptake) to background (venous blood pool) ratio from the aorta obtained via FDG-PET/CT

scans at Week 12. Baseline is defined as the target to background ratio at Visit 2. Patients will be included in the analysis if they have both baseline and post-baseline assessments.

TBRmax (in the dataset) at each visit will be used for analysis. The primary analysis will be based on Full Analysis Set.

### **2.5.2 Statistical hypothesis, model, and method of analysis**

The primary efficacy variable will be analyzed by an analysis of covariance (ANCOVA) model with treatment, baseline, and body weight (<90 kg, ≥90 kg) as explanatory variables.

Following null hypothesis ( $H_0$ ) will be tested against the alternative hypothesis ( $H_A$ ):

$$H_0: \mu_1 - \mu_0 = 0$$

$$H_A: \mu_1 - \mu_0 \neq 0$$

where  $\mu_1$  and  $\mu_0$  denote the population mean of change from baseline in the target to background ratio from the aorta at Week 12 for secukinumab group and placebo group, respectively.

The least squares means of the two treatment groups, least squares mean difference, and 95% confidence interval for the difference in the two treatment groups will be presented along with the p-value based on the fitted linear model.

### **2.5.3 Handling of missing values/censoring/discontinuations**

If a subject has no post-baseline value, the missing value will not be imputed and the subject will be removed from the analysis.

### **2.5.4 Supportive analyses**

A supportive nonparametric analysis will be performed to examine the consistency of results if the assumption of normality for the distribution of the primary efficacy variable is not tenable. For this supportive analysis, the primary efficacy variable will be analyzed using the stratified Wilcoxon rank-sum test with modified ridit scores (van Elteren's test), adjusting for body weight (<90 kg, ≥90 kg) (Stokes, Davis, and Koch, 2012). Supportive analysis will be based on Full Analysis Set.

In addition, changes from baseline in each of the five segments of aorta (ascending aorta, aortic arch, descending thoracic aorta, suprarenal abdominal aorta, infrarenal abdominal aorta) will be analyzed similar to the analyses of the primary efficacy variable.

## **2.6 Analysis of the key secondary objective**

There is no key secondary objective.

## **2.7 Analysis of secondary efficacy objectives**

Analyses of the secondary efficacy analysis will be based on Full Analysis Set.

### **2.7.1 Secondary efficacy variables**

The secondary efficacy variables are the following:

- Change from baseline in each biomarker (specified in Section 2.7.2.1)
- PASI 75 response (yes, no)

- PASI 90 response (yes, no)
- PASI 100 response (yes, no)
- IGA mod 2011 score of 0 or 1 (yes, no)
- Change from baseline in DLQI total score

## **2.7.2 Statistical hypothesis, model, and method of analysis**

### **2.7.2.1 Cardiometabolic Biomarkers**

Change from baseline in each cardometabolic biomarker, described in Section 2.12, will be analyzed at each time point using the same ANCOVA model as for the primary efficacy variable.

In addition, change from the baseline in each biomarker will be analyzed using the stratified Wilcoxon rank-sum test with modified ridit scores (van Elteren's test), adjusting for body weight (<90 kg, ≥90 kg) (Stokes, Davis, and Koch, 2012) if the normality assumption for the variable is not tenable. The analysis will be based on Full Analysis Set.

#### **2.7.2.2 Psoriasis Area and Severity Index (PASI)**

PASI 75 / 90 / 100 responses will be analyzed at each time point using the Cochran-Mantel-Haenszel test to compare secukinumab and placebo, adjusting for body weight (<90 kg, ≥90 kg) (Stokes, Davis, and Koch, 2012). A 95% confidence interval for the difference between the two treatment groups in the proportion of subjects who are responders will be calculated using the normal approximation to the binomial distribution.

In addition, the PASI responses by visit will be summarized by treatment.

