Purpose and rationale	Secukinumab targets Interleukin 17a (IL-17a), which is increasingly understood to be a critical component of the pathophysiology of psoriasis, and evolving research also suggests that IL-17 may promote cardiovascular disease. This study will provide a comparison of secukinumab to placebo with respect to aortic vascular inflammation at 12 weeks of treatment, and up to 52 weeks of treatment in subjects with moderate to severe plaque psoriasis.
Primary Objective(s)	To evaluate the effect of secukinumab compared to placebo on aortic vascular inflammation with respect to the change from baseline in the target (arterial vascular uptake) to background (venous blood pool) ratio from the aorta
Secondary Objectives	
• To evaluate the effect of secukinumab compared to placebo with respect to change from baseline in cardiometabolic biomarkers (cardiometabolic function [lipid particle size, HDL function (cholesterol efflux)], measures of inflammation [TNF-Alpha, IL-6, C-reactive protein, GlycA], adiposity [leptin and adiponectin], insulin resistance [insulin levels/glucose to yield HOMA-IR], and markers predictive of diabetes [apolipoprotein B, ferritin, IL-2 receptor A, IL-18, and fetuin-A]) at Week 12• To evaluate the effect of secukinumab compared to placebo in subjects with moderate to severe chronic plaque-type psoriasis with respect to change from baseline in the PASI 75, 90 and 100 response rates at Week 12• To evaluate the effect of secukinumab compared to placebo in subjects with moderate to severe chronic plaque-type psoriasis with respect to the Investigator's Global Assessment mod 2011 (IGA mod 2011) 0 or 1 response at Week 12

	
• To evaluate the effects of secukinumab compared to placebo with respect to change from baseline in the Dermatology Life Quality Index (DLQI) total score at Week 12• To evaluate the clinical safety and tolerability of secukinumab as assessed by vital signs, clinical laboratory variables, and adverse event monitoring

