3.1.3 Double-blind induction period (Week 12 dose through Week 15 dose)

All subjects who complete the Double-blind Treatment Period will enter the Double-blind Induction Period.

During the Double-blind Induction Period, subjects randomized to placebo during the Double-blind Treatment Period will be switched over to treatment with secukinumab 300 mg. The Double-blind Induction Period is defined as the Week 12 dose through the Week 15 dose. **Subjects must administer the Week 12 dose no later than 7 days after the Week 12 FDG-PET/CT scan.**

- **Secukinumab:** Subjects who were randomized to the secukinumab treatment group at Visit 2/Baseline will continue to self-administer secukinumab 300 mg (two s.c. injections of the 150 mg dose) at Week 12. In order to maintain the blind, these subjects will undergo a sham induction with weekly placebo injections at Weeks 13, 14, and 15.
- **Placebo:** Subjects who were randomized to the placebo treatment group at Visit 2/Baseline will begin to self-administer secukinumab 300 mg (two s.c. injections of the secukinumab 150 mg dose) weekly for four weeks at Weeks 12, 13, 14, and 15.

Self-administration of the Week 12 dose will take place at the study site, while the doses at Weeks 13, 14, and 15 will be self-administered at home.

All subjects who discontinue study treatment prematurely for any reason before the end of Double-blind Induction Period should return to the study site for the performance of the Visit 14/Week 52 End of Treatment 2 (EOT2) assessments. The EOT2 visit should be scheduled 28 days (± 7 days) after the last dose of study treatment.

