3.2 Rationale of study design

The randomized, double-blind, placebo-controlled design used in this study is aligned with the Phase III trials of secukinumab, and with previous studies performed in the indication of chronic plaque psoriasis, and is in accordance with health authority guidelines and feedback, including the United States Food and Drug Administration (FDA).

The study population consists of adult subjects with moderate to severe plaque-type psoriasis who are candidates for systemic therapy or phototherapy.

The primary analysis time point of the trial is at Week 12. This is in line with the timing of the primary analysis time point in the secukinumab Phase III trials, and will allow for assessment of

efficacy at a point in time for which efficacy data from currently approved biologic therapies are available. However, as the study design provides for treatment duration of up to 52 weeks, it also allows for the assessment of longer-term safety and tolerability of secukinumab in this population. For subjects randomized to receive placebo at Visit 2/Baseline, the 52-week treatment duration allows these subjects the opportunity to receive up to 40 weeks of treatment with secukinumab.

Patients with moderate to severe psoriasis have a clinically significant increased risk of major cardiovascular events and mortality independent of traditional risk factors. Treatments that improve not only the skin manifestations of psoriasis but also its cardiovascular co-morbidities are of intense clinical and scientific interest. Measurement of aortic inflammation by FDG-PET/CT is a reproducible, operator independent, prognostic marker of future vascular events (Figueroa et al 2013; Mehta et al 2012). Furthermore, it responds to statins and modulates in a short time frame (i.e., within 12 weeks) unlike alternative approaches such as carotid intima-media thickness (IMT) and MRI-based measures of wall thickness (Tawakol et al 2013).

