5.2 Treatment groups

At Visit 2/Baseline, eligible subjects will be randomized to one of the following two treatment groups in a ratio of 1:1, with approximately 42 subjects per group:

1. **Secukinumab group:** Subjects (or trained caregivers) will self-administer (or administer to the subject) a dose of secukinumab 300 mg s.c. (two injections of the 150 mg prefilled

syringes) once weekly for five weeks (at Randomization, Weeks 1, 2, 3, and 4), followed by dosing every four weeks, starting at Week 8 through Week 48. In order to maintain the blinding during the Double-blind Induction Period, placebo s.c. doses (two injections of the placebo to 150 mg prefilled syringe) will be self-administered by the subjects (or trained caregivers) at Weeks 13, 14 and 15.

2. **Placebo group:** Subjects (or trained caregivers) will self-administer (or administer to the subject) a dose of placebo s.c. (two injections of the placebo prefilled syringes) once weekly for five weeks (at Randomization, Weeks 1, 2, 3, and 4), followed by a dose after four weeks at Week 8.

Beginning at Week 12, all subjects in the placebo group will be switched to treatment with secukinumab 300 mg s.c. Subjects will receive a dose of secukinumab 300 mg s.c. once weekly for five weeks (at Weeks 12, 13, 14, 15, and 16) followed by dosing every four weeks, starting at Week 20 through Week 48.

All subjects who enter the Double-blind Induction Period will self-administer the Week 12 dose following the completion of all assessments scheduled to be performed at Visit 8/Week 12 (Table 6-1).

The treatment groups and dosing frequency are also described in Table 5-1 below.

Table 5-1 Overview of study treatment

Treatment group	DB Treatment Period (Rand – Wk 12 pre-dose)	DB Induction Period (Wk 12 – Wk 15)	OL Treatment Period (Wk 16 – Wk 52)
Secukinumab 300 mg	2x s.c. secukinumab 150 mg injection at Rand, Wks 1, 2, 3, 4 and 8	2x s.c. secukinumab 150 mg injection at Wk 12 2x s.c. secukinumab 150 mg PBO injection at Wks 13, 14 and 15	2x s.c. secukinumab 150 mg injection at Wks 16 - 48
Placebo (PBO)	2x s.c. secukinumab 150 mg PBO injection at Rand, Wks 1, 2, 3, 4 and 8	2x s.c. secukinumab 150 mg injection at Wks 12, 13, 14, and 15	2x s.c. secukinumab 150 mg injection at Wks 16 – 48

DB = Double-blind; OL = Open-label; Rand = Randomization; Wk = Week

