### **Secondary objectives**

- To evaluate the effect of secukinumab compared to placebo with respect to change from baseline in cardio metabolic biomarkers (cardio metabolic function [lipid particle size, HDL function (cholesterol efflux)], measures of inflammation [TNF-Alpha, IL-6, C reactive protein, GlycA], adiposity [leptin and adiponectin], insulin resistance [insulin levels/glucose to yield HOMA-IR], and markers predictive of diabetes [apolipoprotein B, ferritin, IL-2 receptor A, IL-18, and fetuin-A]) at Week 12
- To evaluate the effect of secukinumab compared to placebo in subjects with moderate to severe chronic plaque-type psoriasis with respect to change from baseline in the PASI 75, 90 and 100 response rates at Week 12
- To evaluate the effect of secukinumab compared to placebo in subjects with moderate to severe chronic plaque-type psoriasis with respect to the Investigator's Global Assessment mod 2011 (IGA mod 2011) 0 or 1 response at Week 12
- To evaluate the effects of secukinumab compared to placebo with respect to change from baseline in the Dermatology Life Quality Index (DLQI) total score at Week 12

- To evaluate the clinical safety and tolerability of secukinumab as assessed by vital signs, clinical laboratory variables, and adverse event monitoring.

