**Table 1-1 Assessment windows for PASI and IGA assessment:**

Analysis Visit	Week	Scheduled Day	Visit Window
Baseline	BSL	1	-28 day to Day 1
Week 4	4	29	Day 2-43
Week 8	8	57	Day 44-71
Week 12	12	85	Day 72-99
Week 16	16	113	Day 100-141
Week 24	24	169	Day 142-197
Week 32	32	225	Day 198-253
Week 40	40	281	Day 254-309
Week 48	48	337	Day 310-351
Week 52	52	365	Day >=352

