#### **2.7.2.3 Investigator's Global Assessment (IGA mod 2011)**

IGA mod 2011 (0 or 1) response will be analyzed at each time point using the Cochran-Mantel-Haenszel test to compare secukinumab and placebo, adjusting for body weight (<90 kg, ≥90 kg). A 95% confidence interval for the difference between the two treatment groups in the proportion of subjects who are responders will be calculated using the normal approximation to the binomial distribution. In addition, the IGA mod 2011 responses by visit will be summarized by treatment.

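### 24 of the 36 planned PASI and IGA tests of secukinumab against placebo (Weeks 16 to 52) come after continuing placebo subjects have switched, so they compare immediate with delayed start

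*SAP*

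**What the plan says.** For PASI 75, 90 and 100, SAP 2.7.2.2 states that responses "will be analyzed at each time point using the Cochran-Mantel-Haenszel test to compare secukinumab and placebo", stratified by body weight, with a 95% confidence interval for the difference. SAP 2.7.2.3 reads "IGA mod 2011 (0 or 1) response will be analyzed at each time point using the Cochran-Mantel-Haenszel test to compare secukinumab and placebo". Protocol 9.5.1 has the same plan. None of these sections stops at Week 12. SAP Table 1-1, headed "Assessment windows for PASI and IGA assessment", lists Weeks 4, 8, 12, 16, 24, 32, 40, 48 and 52 after baseline.

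On treatment, Protocol 3.1.3 says "All subjects who complete the Double-blind Treatment Period will enter the Double-blind Induction Period", and Protocol 5.2 says "Beginning at Week 12, all subjects in the placebo group will be switched to treatment with secukinumab 300 mg s.c". Protocol 3.2 adds that the design "allows these subjects the opportunity to receive up to 40 weeks of treatment with secukinumab".

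The comparative efficacy objectives in SAP 1.2 are all set at Week 12; the IGA objective, for example, concerns "0 or 1 response at Week 12". SAP 2.8 renames the second arm *Placebo / Secukinumab 300 mg* for summaries of the entire treatment period, but only for safety. SAP Section 4, which lists departures from the protocol's analyses, does not mention the later efficacy comparisons.

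**The concern.** A test described as secukinumab against placebo should compare people on drug with people on placebo. After Week 12 no continuing subject is on placebo. If the delayed arm catches up, the between-arm difference will shrink towards zero by Week 52. In a table labelled as a placebo comparison, that pattern could be misread as loss of effect.

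The safety and efficacy tables from this one SAP would also name the same subjects differently.

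A new label alone does not settle what the later test estimates. Placebo subjects who stop before Week 12 have an end-of-treatment visit and leave the trial (Protocol 5.5.9), so they never switch. They stay in the Full Analysis Set as randomised. The binary rule in SAP 2.7.3 covers Week 12 and the other time points, so their response status at discontinuation is used at every later visit. The later placebo arm is therefore a mixture of switchers and never-switchers, and the SAP does not say so.

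**Working it through.** The plan states no number of tests, so there is no figure of its own to reproduce for the count. The stated arm size used in step 3 does reproduce: 37 per arm with 10% loss gives 37 / 0.90 = 41.1, rounded up to 42.

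**1. Count of tests.** Inputs: four endpoints (PASI 75, 90, 100 and IGA 0 or 1; SAP 2.7.2.2 and 2.7.2.3) and nine post-baseline visits (SAP Table 1-1). Tests = endpoints × visits, assuming one test per endpoint per visit.

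- All visits: 4 × 9 = 36.
- Weeks 4, 8 and 12: 4 × 3 = 12. Week 12 belongs here because Protocol Table 6-1 puts its assessments before the dose.
- Weeks 16, 24, 32, 40, 48 and 52: 4 × 6 = 24, and 24 / 36 = 67%.
- By measure: PASI 18 of 27, IGA 6 of 9.

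**2. Scheduled secukinumab doses before each later assessment.** Dosing weeks are from Protocol 5.2. The placebo arm receives secukinumab at Weeks 12, 13, 14, 15 and 16, then every four weeks from 20 to 48. The secukinumab arm receives it at Weeks 0, 1, 2, 3 and 4, then every four weeks from 8 to 48. Assessments precede the same-day dose.

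| Week | Placebo arm | Secukinumab arm |
|---|---|---|
| 16 | 4 | 7 |
| 24 | 6 | 9 |
| 32 | 8 | 11 |
| 40 | 10 | 13 |
| 48 | 12 | 15 |
| 52 | 13 | 16 |

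At Week 52 the placebo arm has had 52 − 12 = 40 weeks on secukinumab, which agrees with Protocol 3.2.

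**3. Never-switchers.** The documents do not say when losses occur. If all of the planned 10% fell before Week 12, then 0.10 × 42 = 4.2, so about 4 placebo subjects would never switch and about 38 would. If all losses came later, none would be never-switchers.

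**4. Other endpoints under the same instruction.** SAP 2.7.2.1 and 2.7.2.4 apply the primary two-arm ANCOVA at each time point, without the placebo wording. DLQI has six post-baseline visits (SAP Table 1-2), five of them after Week 12. If all 14 biomarkers (HOMA-IR counted once) are assayed at all six post-baseline draws, there are 14 × 6 = 84 tests, of which 14 × 3 = 42 come after Week 12.

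**5. Fasting (not linked to the switch).** Protocol 6.4.2 requires fasting for biomarker blood draws only at Baseline, Week 12 and Week 52. That leaves 6 − 2 = 4 of six post-baseline draws with no fasting requirement, including Weeks 4 and 8. HOMA-IR is built from insulin and glucose and is to be analysed at each time point. Under the LOCF rule in SAP 2.7.3, a non-fasting Week 8 value could stand in for a missing fasting Week 12 value.

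**The case against.** The strongest reply is that placebo is simply the name of the randomised arm. SAP Table 2-1 and Protocol Table 5-1 keep that name through Week 52 and show the switch in the same row. The Full Analysis Set is analysed as assigned, so a later test by arm is a legitimate randomised comparison of immediate with delayed start, and nothing is miscalculated. SAP 2.7.3 mentions subjects who switch. Response rates by visit and treatment will be tabulated, so a rise in the placebo arm after Week 12 would be visible. No comparative efficacy objective lies beyond Week 12, and there is no key secondary objective.

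Most of this stands. It shows that the later tests are valid and that a careful reader could work out their meaning. It does not show that the SAP says what they estimate: the efficacy sections neither limit nor rename the contrast, whereas the safety section does rename the arm, and never-switchers are not addressed.

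Two stronger readings are tempting and are not supported:

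- A reader might take the Protocol summary's purpose statement, "a comparison of secukinumab to placebo with respect to aortic vascular inflammation at 12 weeks of treatment, and up to 52 weeks of treatment", as promising a 52-week placebo comparison. It concerns aortic inflammation, not PASI or IGA. The full title attaches the placebo comparison to the first 12 weeks and describes the rest as treatment with secukinumab.
- A reader might infer that early leavers' retained status pushes the later differences in a known direction. The documents give no response rates for early leavers. With about 4 of 42 leaving in each arm, arithmetic alone bounds their contribution at ±4/42, or ±9.5 percentage points, and its sign is unknown. Counting them in their assigned arm also follows the stated intent-to-treat rule.

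**Conclusion.** The point holds as one of naming and estimand, not of validity. Of the 36 planned PASI and IGA tests, 24 (67%) are described as placebo comparisons but compare immediate with delayed start, with possibly a few never-switchers in the delayed arm. The count assumes one test per endpoint per visit in SAP Table 1-1. The figure of about four never-switchers assumes that all of the planned loss occurs before Week 12.

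The primary analysis and the observed Week 12 results are unaffected, and no objective depends on the later tests. The correction is nearly free and should be made.

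The fasting point is separate and smaller. Non-fasting samples add noise to HOMA-IR change but do not by themselves bias the randomised contrast. Its one route into a Week 12 secondary result is a carried-forward non-fasting value. The laboratory manual was not available, so any fasting instruction it contains could not be checked.

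A further minor point, of unknown size: SAP 2.7.3 bars carrying period 1 DLQI and biomarker values into period 2 only for subjects who switch, so subjects in the same later ANCOVA are handled differently. The end-of-treatment visits and the multiple imputation added in SAP Section 4 reduce its effect.

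**What to change.** 1. In SAP 2.7.2.1 to 2.7.2.4, limit secukinumab-versus-placebo inference to visits through Week 12 pre-dose. For PASI and IGA this leaves the 12 tests at Weeks 4, 8 and 12.
2. For later visits, use the SAP 2.8 labels *Secukinumab 300mg* and *Placebo / Secukinumab 300 mg*. Either report estimates within each treatment sequence with 95% confidence intervals, or keep the between-arm test and name it immediate versus delayed start. In both cases, state how placebo subjects who never switched are counted.
3. Record this in SAP Section 4 as a change to Protocol 9.5.1.
4. Separately, analyse HOMA-IR, insulin and glucose only at Baseline, Week 12 and Week 52, and do not carry a non-fasting value by LOCF into Week 12 or Week 52.

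The cost is revised wording, table labels and one Section 4 entry. No new data are needed. The sponsor gives up some later p-values and the intermediate HOMA-IR results.
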